### **8.4.3 Missing Data**

A participant who withdraws from the study for any reason will be included in the analyses regardless of time on study. Methods for handling withdrawals and missing data will be specific to each endpoint to be analyzed. Details will be provided in the SAP.

## **8.5 Analyses of Safety**

### **8.5.1 Study Drug Exposure**

For FCM, the number of infusions and total administered amount of iron will be summarized descriptively. For oral iron, the total amount of iron will be summarized descriptively.

### **8.5.2 Adverse Events**

Adverse events will be coded by system organ class (SOC) and preferred term (PT) using the Medical Dictionary for Regulatory Activities (MedDRA) dictionary.

The number and percent of participants who report TEAE will be summarized for each treatment group. A TEAE is an event with onset date on or after the study drug start date.

Adverse event summaries will exclude preferred terms that describe asymptomatic serum ferritin, TSAT, and reticulocyte values (or changes). This approach is justified by the reporting of these values in efficacy summaries and is consistent with the protocol-defined reporting standards for hemoglobin/hematocrit and low iron indices. For the purposes of this study, non-serious anemia (hemoglobin or hematocrit below the normal range or worsened from baseline) or iron deficiency (iron indices below the normal range or worsened from baseline) will not be considered adverse events. Anemia or iron deficiency will be considered end points if an intervention is required.

The adverse event profile will be characterized with severity (as graded by the National Cancer Institute Common Terminology Criteria for Adverse Events [NCI-CTCAE]) and relationship (unrelated and related) to study drug. Related adverse events will be events that are possibly or probably related to treatment in the investigator's judgment.

Participants who report the same preferred term on multiple occasions will be counted once for the preferred term: under the highest severity when summarized by severity and under the closest relationship to study drug when summarized by relationship. If a participant reports multiple preferred terms for a SOC, the subject will be counted only once for that SOC.

The number and percent of participants who report treatment-emergent serious adverse events will be similarly summarized for each treatment group. The number and percent of participants who report treatment-emergent adverse events resulting in discontinuation of study drug will be similarly summarized for each treatment group.

### **8.5.3 Adverse Events of Special Interest**

Adverse events (AEs) of special interest include hypersensitivity, hypersensitivity-like reactions, and cardiovascular events. Hypersensitivity and hypersensitivity-like reactions will be identified using standardized MedDRA queries. Cardiovascular events will be identified using the SOCs for cardiac disorders and vascular disorders.

The overviews and summaries that are provided for all TEAEs will also be provided for the AEs of special interest. In addition, the time to onset and time to recovery will be summarized.

### **8.5.4 Clinical Laboratory Findings**

Clinical laboratory variables will be presented in two ways. First, the mean change from baseline to each scheduled visit will be summarized. Second, the number and percent of participants with treatment-emergent PCS laboratory values will be tabulated. Treatment-emergent PCS laboratory tests are those in which the baseline value is normal and post-baseline value is abnormal (i.e., meets Grade III or Grade IV toxicity criteria from the NCI-CTC Version 5 or higher). Baseline will be defined as the last value obtained before randomization.

No formal statistical tests will be performed.

### **8.5.5 Vital Signs**

For the FCM group, the change in vital signs (including sitting heart rate and blood pressure) from pre-infusion to each post-infusion time point will be summarized descriptively on each dosing day.

### **8.6 Sample Size Rationale**

A total of 60 participants (30 per treatment group) are required to detect an expected difference in hemoglobin of 1.0 g/dL (common standard deviation = 1.16 g/dL) at two-sided  $\alpha=0.05$  with 90% power. Assuming 20% attrition of subjects not meeting the definition of mITT, approximately 72 participants will be randomized.

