**Study Sites:**

Approximately 30

**Participant Number:** Approximately 72 randomized (N=36 FCM / N=36 Oral Iron)

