**Sample Size Rationale:**

A total of 60 participants (30 per treatment group) are required to detect an expected difference in Hgb of 1.0 g/dL (common standard deviation = 1.16 g/dL) at two-sided alpha = 0.05 with 90% power.

Assuming 20% attrition of subjects not meeting the definition of modified intention to treat (mITT), approximately 72 participants will be randomized.

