### **8.4 Endpoints and Definitions**

#### **8.4.1 Primary Endpoint**

The primary endpoint is the change in hemoglobin from baseline to day 35. The change in hemoglobin from baseline to day 35 will be analyzed using parametric analysis of covariance (ANCOVA). The model will include terms for the randomization strata (hemoglobin and age categories), baseline hemoglobin, as well as treatment group. Baseline hemoglobin will be defined as the last hemoglobin obtained before randomization.

The primary endpoint will be analyzed for the mITT population.

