### 1.3.4 Sample Size and Statistical Power Considerations

A total of 60 participants (30 per treatment group) are required to detect an expected difference in hemoglobin of 1.0 g/dL (common standard deviation = 1.16 g/dL) at two-sided  $\alpha=0.05$  with 90% power. Assuming attrition of subjects not being evaluable for efficacy analysis, approximately 72 participants will be randomized.

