## 9. SUMMARY OF MAJOR CHANGES IN THE PLANNED ANALYSES

Compared with the study protocol (26SEP2019 Administrative Change 1), below items are the major changes made in this SAP:

1. The efficacy analyses will be conducted for the ITT population instead of the mITT population to be more in keeping with accepted practice. The mITT population will still be defined and will be used for post-hoc sensitivity analyses.
2. In protocol, the sentence of “Changes from baseline in hemoglobin, ferritin, TSAT, and reticulocyte hemoglobin content throughout the study” in [section 8.4.2](#) is not consistent with the sentence in study synopsis. In this SAP, we just keep this endpoint in consistency with descriptions in synopsis.
3. To assess the robustness of primary and secondary efficacy analysis, supportive analyses will be performed using MMRM model.
4. The scale defined in Division of AIDS (DAIDS) Table for Grading the Severity of Adult and Pediatric Adverse Events, Version 2.1 from March 2017 (Division of AIDS, National Institute of

Allergy and Infectious Diseases, National Institutes of Health, US Department of Health and Human Services) will be used to identify abnormal clinical laboratory values instead of toxicity criteria from the National Cancer Institute Common Terminology Criteria version 5 for Adverse Events specified in the protocol.

5. The subgroups Cause of IDA: IBD, not IBD and CKD, not CKD are not included in this SAP because of insufficient sample size for meaningful estimates.

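### Protocol 8.6 and synopsis: 20% attrition from 72 randomized leaves about 57–58 in the mITT population, not the required 60; 72 allows only 16.7%

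*Protocol*

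**What the plan says.** Protocol 8.6 gives the requirement: "A total of 60 participants (30 per treatment group) are required to detect an expected difference in hemoglobin of 1.0 g/dL", with a common SD of 1.16 g/dL, two-sided alpha of 0.05 and 90% power. It then sets the number to randomize: "Assuming 20% attrition of subjects not meeting the definition of mITT, approximately 72 participants will be randomized". The synopsis repeats this: "Assuming 20% attrition of subjects not meeting the definition of modified intention to treat (mITT), approximately 72 participants will be randomized". The synopsis entry for participant number splits the 72 as 36 per arm.

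The population matters here. Protocol 8.4.1 says: "The primary endpoint will be analyzed for the mITT population". The mITT population (Protocol 8.2) is the subset of randomized participants with at least one dose, a baseline hemoglobin and at least one post-baseline hemoglobin.

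The SAP changes this. Section 9 says: "The efficacy analyses will be conducted for the ITT population instead of the mITT population to be more in keeping with accepted practice". SAP 2.3.4 and 6.1.1 impute missing values in the primary ANCOVA. SAP 1.3.4 keeps 60 and 72 but gives no percentage: "Assuming attrition of subjects not being evaluable for efficacy analysis, approximately 72 participants will be randomized".

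**The concern.** A sample-size rationale should let the reader go from the number required, through the assumed loss, to the number randomized. Here that step fails. In the protocol, attrition means randomized participants who do not qualify for the mITT population, so the 20% is a share of those randomized. The figure 72 instead comes from adding 20% to the required 60, which is not the same calculation.

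At the loss the protocol itself plans for, its primary population would fall 2–3 participants short of the number it calls required. The stake is the accuracy of the justification, which appears twice. It is not a material loss of power.

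**Working it through.** **Inputs** (Protocol 8.6 and synopsis): difference 1.0 g/dL; SD 1.16 g/dL; two-sided alpha 0.05; power 90%; 1:1 allocation; 60 required; 20% attrition; 72 randomized (36 per arm).

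**1. Reproduce the 60.** By normal approximation, n per arm = 2 × (1.960 + 1.282)² × 1.16² / 1.0² = 28.3, so 29 per arm (58 in total). By two-sample t-test, n per arm = 29.3, so 30 per arm. The stated 60 reproduces. If unequal arms are allowed, the smallest total with at least 90% power by t-test is 59 (29 + 30).

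**2. Try to reproduce the 72.**
- Loss taken from those randomized: 60 / (1 − 0.20) = 75, or 76 with equal arms (30 / 0.80 = 37.5, so 38 per arm).
- 20% added to the required number: 60 × 1.20 = 72.

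Only the second gives the stated figure.

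**3. What 72 delivers.**
- Loss at 20%: 72 × 0.20 = 14.4.
- Remaining: 72 × 0.80 = 57.6 (28.8 per arm), so about 57–58.
- Loss that keeps 60: 72 − 60 = 12, and 12/72 = 16.7%.
- Loss that keeps 59: 72 − 59 = 13, and 13/72 = 18.1%.

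**4. Effect on power** (difference 1.0, SD 1.16, two-sided 0.05):

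| Total (arms) | t-test | Normal approximation |
|---|---|---|
| 60 (30 + 30) | 90.7% | 91.6% |
| 59 (29 + 30) | 90.2% | – |
| 58 (29 + 29) | 89.7% | 90.7% |
| 57.6 (28.8 + 28.8) | 89.5% | 90.5% |
| 57 (28 + 29) | 89.2% | 90.2% |

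At 57–58 participants, power is 0.3–0.8 points below 90% by t-test and is not below 90% by normal approximation. The difference detectable with 90% power by t-test goes from 0.987 g/dL at 30 + 30 to 1.005 at 29 + 29 and 1.014 at 28 + 29.

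**5. Which analyses this touches.** It concerns the protocol's mITT primary plan. In the SAP's imputed ITT ANCOVA all 72 randomized participants count, so the shortfall does not arise there. SAP 1.3.4 states no percentage and so contains no arithmetic error.

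**The case against.** The strongest reply is that little follows from this.

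- **The required number is itself rounded up.** The t-test needs 58.5 in total (2 × 29.3), and the normal approximation is met by 58, for which 58 / 0.80 = 72.5. The protocol does not name its sample-size method, so whether any power is lost depends on the method chosen. The number randomized is also only approximate. This limits the size of the problem, but the protocol states 60 as the requirement, and 72 is exactly 60 × 1.2.
- **The planned analysis is an ANCOVA, not a t-test.** If 1.16 is an unadjusted SD, which the documents do not say, covariates explaining about 1.5% of the variance restore 90% at 29 + 29, and about 3% do so at 28 + 29, after allowing three extra degrees of freedom. If 1.16 is already a residual SD, there is no such gain. Either way this bears on power and does not make 60, 20% and 72 agree.
- **The SAP has moved on.** It drops the 20% and makes ITT with imputation primary. The mITT population remains only for sensitivity use: "The mITT population will still be defined and will be used for post-hoc sensitivity analyses". That protects the primary result. However, the changes listed in SAP section 9 do not include the sample-size rationale, and the protocol sentences stand uncorrected.

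These points settle the weight: a small correction of text, not a power problem.

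**Conclusion.** The concern holds. With 72 randomized and 20% outside the mITT population, about 57–58 participants remain, 2–3 fewer than the 60 stated as required; 72 supports 16.7% attrition. Power moves by less than one point from 90%, on the protocol's own difference and SD and a two-group comparison without covariate gain. The SAP's imputed ITT primary analysis is not affected, and nothing here shows that the trial is underpowered.

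**What to change.** Do not enrol more. Change one sentence in Protocol 8.6 and the matching sentence in the synopsis, in one of two ways:

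- **Preferred:** say that randomizing 72 allows up to 16.7% (12 participants) not to meet the mITT definition while keeping 60. This makes all three figures agree and leaves the preceding sentence as it is.
- **Alternative:** keep 20%, and say that it leaves about 57–58 in the mITT population with about 89–90% power. The preceding sentence, which calls 60 the requirement, would then also need adjusting.

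The cost is a lower stated attrition allowance or a slightly lower stated power, with no change to enrolment or analysis. Protocol 9.8.5 lets a clarification go in a numbered memo.

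Optionally, SAP 1.3.4 could note that its allowance for non-evaluable participants concerns analyses without imputation, not the imputed ITT ANCOVA. The losses differ between those analyses: falling outside the mITT population is not the same as missing only the Day 35 value. If an ITT power figure is added (95.0% by t-test at 36 per arm), label it as assuming that the 1.0 g/dL difference and 1.16 g/dL SD still hold after imputation. The core correction does not depend on this note.

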## **9.0 ADMINISTRATIVE CONSIDERATIONS**

### **9.1 Retention and Availability of Records**

Investigators are required to maintain all study documentation, including a copy of the eCRFs, Informed Consent documents, and adequate records for the receipt and disposition of study medications, for a period of two years following a supplemental application for the drug for the indication being investigated, or until two years after the drug investigational program is discontinued.

The Investigator must make study data accessible to the monitor, Sponsors, or other authorized representatives of the Sponsor and Regulatory Agency (i.e., FDA inspectors.) A case history for each participant must be maintained, and this should include the signed Informed Consent form and copies of all study documentation related to that participant. The investigator must ensure the availability of source documents including the electronic health record, if applicable, from which the information on the eCRF was derived.

### **9.2 Investigator Responsibilities**

By signing the Form FDA 1572 the Investigator agrees to:

1. Conduct the study in accordance with the protocol and only make changes after notifying the Sponsor, except when necessary to protect the safety, rights or welfare of participants.
2. Personally conduct or supervise the study (or investigation).
3. Inform any participants that the drug is being used for investigational purposes.
4. Ensure that the requirements relating to obtaining informed consent and IRB review and approval meet Federal guidelines, as stated in 21 CFR, parts 50 and 56.
5. Report to the Sponsor any adverse events that occur in the course of the study, in accordance with 21 CFR 312.64.
6. Have read and understood the Investigator's Brochure, including potential risks and side effects of the drug.

7. Ensure that all associates, colleagues, and employees assisting in the conduct of the study are informed about their obligations in meeting the above commitments.
8. Maintain adequate and accurate records, in accordance with 21 CFR 312.62, and to make those records available for inspection with the Sponsor, their designated representative, the FDA or any agency authorized by law.
9. Ensure that an IRB that complies with the requirements of 21 CFR Part 56 will be responsible for initial and continuing review and approval of the clinical study.
10. Promptly report to the IRB and the Sponsor all changes in the research activity and all unanticipated problems involving risks to participants or others (including amendments and IND safety reports).
11. Not make any changes in the research study without approval, except when necessary to eliminate hazards to the participant/participants.
12. To comply with all other requirements regarding the obligations of the clinical investigators and all other pertinent requirements listed in 21 CFR Part 312.

### **9.3 Financial Disclosure**

All principal investigators and co-investigators will be required to complete FDA-required financial forms provided by American Regent, Inc. All signed financial disclosure forms must be submitted to the Sponsor prior to the site enrolling participants into the study.

### **9.4 Advertisement for Participant Recruitment**

All advertisement for participant recruitment must be reviewed and approved by the Sponsor and the site's IRB prior to implementation. Advertisement may include but is not limited to: newspaper, fliers, radio, and television. Any compensation to the participant included in the advertisement must be identical to the compensation stated in the IRB-approved informed consent.

### **9.5 Documents Required for Study Initiation**

Prior to study initiation, the investigator must provide American Regent, Inc. or its designee with the following documentation:

- Curriculum Vitae and medical licenses for Principal Investigators and co-investigators.
- Form FDA 1572
- Financial disclosure form(s)
- IRB approval of protocol and informed consent
- Copy of IRB approved informed consent
- IRB membership list or assurance number
- Protocol signature page
- IRB approval of any advertising for participant recruitment [if applicable]
- Copy of advertising [if applicable]

- IRB approval of translation of informed consent [if applicable]

## **9.6 Quality Control and Quality Assurance**

### **9.6.1 Investigator Selection Criteria**

Each investigator participating in this study will meet the following criteria:

- Accessible, interested, and available support staff.
- Availability of adequate facilities to support study requirements.
- Availability of physician emergency response at all times.
- Adequate time to conduct study.
- Adequate training and experience of personnel to conduct study.
- Ability to recruit enough participants to conduct study.

Prior to investigator selection, each site will be evaluated to ensure they meet the criteria noted above.

American Regent, Inc. and/or their designee will insure that no investigator is on FDA's Debarment List or Disqualified Investigator List.

### **9.6.2 Clinical Monitoring**

This study will be monitored by the Sponsor (or its designee) in accordance with FDA and International Conference on Harmonisation Good Clinical Practices (GCPs), 21CFR Part 312. As part of a concerted effort to follow the study in a detailed and orderly manner, and in accordance with established principles of GCP and applicable regulations, a Monitor will visit the site according to the monitoring plan and will maintain telephone and written communication throughout the duration of the study.

### **9.6.3 Quality Assurance Audit**

For the purpose of data validation, the principal investigators will permit a member of the quality assurance unit of American Regent, Inc. or its designee to inspect the source data and compare them with the eCRFs. Pre-study audits, interim audits, and post-study audits may be performed and these may include a review of facilities, equipment, pertinent site documentation, and personnel qualifications. Notification of these audits will be sent to investigators in advance.

## **9.7 Ethics**

### **9.7.1 Ethical and Legal Issues**

This study will be performed in accordance with the U.S. Code of Federal Regulations on Protection of Human Participants (21 CFR 50), IRB regulations (21 CFR 56), the most recent revision of the Declaration of Helsinki, all applicable local and state regulations, 21 CFR Part 312, and applicable ICH guidelines.

### **9.7.2 Institutional Review Board**

The Protocol and the Informed Consent must be approved by an appropriate Institutional Review Board (IRB) before the study is initiated. Documentation of this approval must be provided to the Sponsor or designee. The IRB must comply with current U.S. Regulations (21 CFR 56) for the protection of Human Subjects in Research. Investigators are responsible for the following:

- Obtain IRB approval of the protocol, Informed Consent, and any advertisements to recruit participants; obtain IRB approval for any protocol amendments and Informed Consent revisions before implementing the changes.
- Provide the IRB with any information it requests before or during the study.
- Submit progress reports and a final report to the IRB, as required, during the conduct of the study; request re-review and approval of the study as needed; provide copies of all IRB re-approvals and relevant communication with the Sponsor.
- Notify the IRB of all serious adverse events that occur or are reported to you by the Sponsor as required by the IRB.

### **9.7.3 Informed Consent**

Informed consent / Assent (when appropriate) must be obtained from each participant prior to study participation. The informed consent / assent will be provided to the participant in their native language. The consent/assent form must be signed by the participant and/or the participants legally authorized representative. Each investigational site must provide the Sponsor (or designee) with a copy of the Informed Consent / Assent approved by that site's Institutional Review Board. The original signed consent / assent form will be retained in the participant's study records, and a copy will be provided to the participant. The Clinical Monitor will assure that each Informed Consent / Assent meets the requirements of Parts 50.20 and 50.25 of Title 21 of the CFR, which outlines the basic elements of informed consent and ICH guidelines. Translations of the informed consent / assent must be certified by a qualified translator and their use must be documented.

The Informed Consent / Assent documents the information that the Investigator provides to the participant and the participants agreement to participate. The Investigator will fully explain the nature of the study, along with the aims, methods, anticipated benefits, potential hazards and discomfort that participation might entail. The Informed Consent / Assent must be signed and dated by each participant and/or legal representative before entering the study and prior to the performance of any study specific procedures.

### **9.7.4 Good Clinical Practice**

The conduct of the study will conform with the recommendations for clinical studies in humans as set out in the most current revision of the "Declaration of Helsinki", the local

legal requirements and the guidelines on “Good Clinical Practice”, [21 CFR Part 312 and ICH guidelines].

